6.2 Pharmacokinetics/Pharmacodynamics

Pharmacokinetic/pharmacodynamic analysis will be performed on the PK and PD Populations respectively

Plasma samples will be analyzed for bexagliflozin concentrations using a validated method.

Blood samples for PK analysis will be collected at pre-dose and at 0.5, 1, 2, 3, 4, 5, 6, 8, 10, 12, 16, 24, 36, and 48 h post dose.

Urine samples for PD analysis will be collected prior to dosing (-12 to 0 h) and in the following intervals after dosing: 0–12, 12–24, 24–36, and 36–48 h.

6.3 Safety

Safety analysis will be performed on the Safety Population.

The safety profile of bexagliflozin will be assessed through the recording, reporting, and analyzing of AEs, clinical evaluations (PE results, VS results, ECG results), and clinical laboratory testing.

Safety variables include the following:

1. AEs
2. Clinical laboratory measurements – serum chemistry, hematology, and urinalysis
3. Urine drug screen
4. VS
5. ECG
6. PE
7. Pregnancy test
8. Concomitant medications/treatments

6.3.1 Study Day and Visit Window Definitions

Refer to Section 6.1.1 for details.

6.3.2 Extent of Exposure to Study Medication

This is a single dose study. Subjects will receive a single dose of 20 mg of bexagliflozin.

6.3.3 Adverse Events (AEs)

Adverse events will be collected and coded using version 21.0 (or newer) of MedDRA. Analysis of AEs will be carried out on the Safety Population. All AEs will be included in the individual subject data listings. Only treatment emergent adverse events (TEAEs) will be tabulated in summary tables. The incidence of TEAEs will be presented by hepatic function group.

If the AE(s) onset date-time or date occurs after the dose of bexagliflozin up until the end of the study, the AE(s) will be assigned to bexagliflozin.

All adverse events will be assessed by the investigator(s) with respect to severity, relationship to study drug and seriousness.

6.3.3.1 Treatment-Emergent AE (TEAE)

An adverse event is considered treatment-emergent if it occurs after treatment with the study drug, and if the date of onset is on or after the date of the dose of study medication, or worsens during the treatment period (intensity/severity grades worsen).

6.3.3.2 Serious Adverse Events (SAE)

AEs will be categorized as serious or non-serious using the definition specified in Section 6.7 of the study protocol.

6.3.3.3 Immediately Reportable AE (IRAE)

An IRAE is any serious adverse event that is reported within 24 hrs of the site being aware of the event.

6.3.3.4 Adverse Events Counting Rules

1. A subject with more than one different AE in a particular system organ class (SOC) will be counted only once in the total of subjects experiencing adverse events in that particular SOC.
2. A subject having experienced the same event (AE preferred term [PT]) more than once during the study will be counted only once in the number of subjects with that event.
3. For a subject who experienced the same event (AE preferred term) more than once during the study with a different severity or seriousness, the AE will be counted only once with the worst grade and seriousness respectively.
4. For a subject who experienced the same event (AE preferred term) more than once during the study with a different causal relationship to the study drug, the AE will be counted only once by considering the most-related documented degree of relationship.

6.3.3.5 AE Severity

Adverse events will be graded on a 3-point scale and reported as indicated on the case report form (CRF). The intensity of an adverse experience will be graded as Grade 1 “Mild”, Grade 2 “Moderate”, and Grade 3 “Severe” using the criteria specified in Section 6.7 of the study protocol.

6.3.3.6 Relationship to the Investigational Medicinal Product

The relationship of an AE to dosing will be assessed as “Definite”, “Probable”, “Possible”, “Not Likely”, or Unrelated using the criteria specified in Section 6.7 of the study protocol.

6.3.3.7 AE with Irregular Start/End Dates or Times

Partial dates or times may be imputed when appropriate. Imputed dates will be used to determine Study Day.

If a partial date and/or time is reported for the start of an AE, a complete date and time will be imputed by the following algorithm:

1. Only the year is reported: If the subject started receiving study drug in the previous year, then January 1 will be used as the starting date of the event. If the subject started receiving study drug in the year reported, then the date of the first dose of study drug will be used as the start date of the event.

2. The month and year is reported: If the subject started receiving study drug prior to the month and year reported, then the first day of the month will be used as the starting date of the event. If the subject started receiving study drug during the month and year reported, then the date of the first dose of study drug will be used as the start date of the event.
3. Time is not reported: If the event date, or imputed date (from rule 1 or 2), is on the same date as study drug start, then time of start of the drug will be used as the start time. For other dates or imputed dates, 12 AM (00:00) will be imputed as the start time.

If a partial date is reported for the end of an AE and the AE is not continuing, a complete date will be imputed by the following algorithm:

1. Only the year is reported: If the subject started receiving study drug in the previous year, then the date of final study contact with the subject will be used as the end of the adverse event. If the subject started receiving study drug in the year reported, then the earlier of December 31 or the date of final study contact with the subject will be used as the end date of the AE.
2. The month and year is reported: The earlier of the last date of the month or the date of final contact with the subject will be used as the end of the AE.
3. Time is not reported: Impute 23:59.

The above rules are subject to logical sense, for example, imputed start date should be on or prior to imputed end date, and end time must equal or exceed start time, if on the same date and end time should equal or exceed start time on the same date.

All AEs will be included in the listings regardless the completeness of the onset dates.

6.3.4 Laboratory Data

Clinical laboratory tests on hematology, serum chemistry, and urinalysis will be performed according to the schedule in Section 3.6. Investigators will assess whether there are any clinically significant abnormalities and record the abnormality on medical history or AE forms.

Conversion to the International System of Units

All laboratory data will be stored in the database with the units in which they are originally reported. Laboratory data in summary tables and subject data listings will be presented in the International System of Units (SI units; *Système International d'Unités*). Laboratory data not reported in SI units will be converted to SI units before further processing or data analysis.

Abnormal Values

Based upon laboratory normal ranges, laboratory test results will be categorized according to the normal range as low, normal and high. Subjects with laboratory data outside the normal range will be listed with abnormal values flagged.

Table 3 Clinical Laboratory Tests

Hematology	
Hematocrit (Hct)	Mean corpuscular volume (MCV)
Hemoglobin (Hgb)	Platelet count
Mean corpuscular hemoglobin (MCH)	Red blood cell (RBC) count
Mean corpuscular hemoglobin concentration (MCHC)	White blood cell (WBC) count with differential
International normalized ration (INR)	
Serum Chemistry, Electrolytes, and Lipids	
Albumin (ALB)	Calcium (Ca)
Alanine aminotransferase (ALT)	Magnesium
Aspartate aminotransferase (AST)	Phosphorus
Blood urea nitrogen (BUN)	Potassium (K)
Glucose	Sodium (Na)
Bicarbonate	Total bilirubin
Creatinine	Direct bilirubin
Creatinine kinase	Alkaline Phosphatase (ALP)
Chloride (Cl)	Uric acid
Total protein	Low-density lipoprotein cholesterol (LDL-C), calculated
Total cholesterol (TC)	
High-density lipoprotein cholesterol (HDL-C)	
Triglycerides (TG)	
Urinalysis	
Appearance	Nitrite
Bilirubin	pH
Color	Protein
Glucose	Specific gravity
Ketones	Urobilinogen
Microscopic examination of sediment (performed if protein, leukocyte esterase, nitrite, or blood is positive)	Leukocyte esterase
Occult blood	
Urine Collection	
Glucose	Creatinine
Urine Drug Screen	

Amphetamines	Opiates
Barbiturates	Benzodiazepines
Cocaine Metabolites	Cannabinoids
MDMA	Methamphetamine
TCA	Methadone
PCP	OXY
Alcohol	

Pregnancy Test - Urine

Infectious Disease Testing (measured at screening only)

Hepatitis B Surface Antigen (HbsAg)	Hepatitis C virus (HCV)
Human Immunodeficiency Virus antibody (HIV)	

6.3.5 Vital Signs

Vital signs include pulse (beats/min), SBP and DBP (mmHg), oral temperature (°C) and respiration rate (breaths/min).

Vital sign changes from baseline will be summarized by hepatic function group.

Baseline values are those measured at last evaluation prior to administration of study drug.

Change from baseline to time point t, denoted $Change_t$, will be calculated as:

$$Change_t = Value_t - Value_{Baseline}$$

6.3.6 Electrocardiogram

ECG parameters, including the RR interval (intra-beat interval), PR interval (the period that extends from the beginning of the P wave [the onset of atrial depolarization] until the beginning of the QRS complex [the onset of ventricular depolarization]), QRS interval, QT interval (the corrected QT interval is the measure of the time between the start of the Q wave and the end of the T wave in the heart’s electrical cycle), and QTcB interval will be measured according to the study assessment schedule as specified in Section 3.6.

Each ECG will be assessed by the Investigator for signs of ischemia, clinically significant hypertrophy, and clinically significant T-wave (repolarization of the ventricles) abnormalities. Baseline ECGs will be defined as the last evaluation performed prior to the administration of study drug.

ECG changes from baseline will be summarized by hepatic function group.

Change from baseline to time point t, denoted $Change_t$, will be calculated as:

$$Change_t = Value_t - Value_{Baseline}$$

6.3.7 Physical Examination

A complete PE will include measurement of body weight and height (height will be measured only at screening), general assessment of all body systems including the skin, head, eyes, ears, nose, throat, neck, lungs, heart, abdomen, lymph nodes, and extremities.

Physical examination results will be presented in individual subject data listings.

6.3.8 Pregnancy Test

Only pregnancies considered by the investigator as related to study treatment (e.g., resulting from an interaction between study drug and a contraceptive medication) are considered AEs unto themselves.

6.3.9 Concomitant Medications/Treatments

Concomitant medications administered during the study will be recorded on the CRF. The medication name, indication, dose, unit, frequency, route of administration, start/stop date(s) and time(s) of administration and reason for administration will be recorded. If the concomitant medication is ongoing this will be documented on the CRF. This documentation should continue until discharge from the study.

A concomitant medication is any medication the subject enters the trial taking and is expected to continue taking for some portion of the trial, as well as any medication other than the investigational product that the subject takes during the course of the trial. All prescription and over-the-counter (OTC) medications (non-prescription drugs), including vitamins and herbal supplements, that subjects receive during the trial must be documented on the CRF. This documentation will continue until the subjects are discharged.

Concomitant medications will be coded using the World Health Organization Drug Dictionary (WHO-DD).

All prior and concomitant medication will be presented in individual subject data listings.

For medications with incomplete dates or times, imputation will be used to convert to a complete date and time. Imputed dates will be used to determine Study Day.

Partial medication start dates and times will be imputed as follows:

1. Only the year is reported: If the subject started to receive study drug in the year reported, then the date of the first dose of study drug will be used as the starting date of the medication. Otherwise, January 1 will be used as the start date of the medication.
2. The month and year is reported: If the subject started to receive study drug during the month and year reported, then the date of first dose of study drug will be used as the starting date of the medication. Otherwise, the first day of the month will be used as the start date of the medication.
3. Time is not reported: If the medication start date, or imputed date (from rule 1 or 2), is on the same date as study drug start, then time of start of the study drug will be used as the start time. For other dates or imputed dates, 12 AM (00:00) will be imputed as the start time.

Partial medication end dates and times will be imputed for non-ongoing medications as follows:

1. Only the year is reported: If the subject stopped to receive study drug in the year reported, then the date of the last dose of study drug will be used as the end date of the medication. Otherwise, December 31 will be used as the end of the medication.
2. The month and year is reported: If the subject stopped to receive study drug during the month and year reported, then the date of last dose of study drug will be used as the end date of the medication. Otherwise, the last day of the month will be used as the end of the medication.
3. Time is not reported: Impute 23:59.

The above rules are subject to logical sense, for example, imputed start date should be on or prior to imputed end date.

Verbatim terms will be coded and assigned a preferred (PT) term and an ATC (anatomic therapeutic class) term.

7. PHARMACOKINETIC/PHARMACODYNAMIC ANALYSES

7.1 General Considerations

The PK Population will be used for PK analyses. The PD Population will be used for PD analyses.

Statistical, PK, and PD analyses will be performed by Everest Clinical Research. Statistical analysis will be performed using Statistical Analysis Software SAS for Windows® (SAS Institute Inc., USA). Non-compartmental analysis (NCA) will be performed using Phoenix® WinNonlin® 6.4 (Certara, USA) or later.

7.2 Pharmacokinetic Analyses

From the plasma concentration-time data, the following PK parameters will be estimated for each subject where feasible.

Table 7. Pharmacokinetic Parameters

Pharmacokinetic Parameters	
C_{max}	Maximum observed plasma concentration
T_{max}	Time of maximum observed plasma concentration
λ_z	Terminal elimination phase rate constant
$T_{1/2}$	Apparent terminal elimination half life
CL/F	Apparent oral clearance
V_z/F	Apparent volume of distribution
AUC_{0-24}	Area under the plasma concentration-time curve from the time of dosing to 24 h post-dose
AUC_{0-t}	Area under the plasma concentration-time curve from time 0 to time t (time of last quantifiable plasma concentration)
$AUC_{0-\infty}$	Area under the plasma concentration-time curve from time 0 to infinity
AUC_{extr}	The proportion of $AUC_{0-\infty}$ due to extrapolation from T_{last} to infinity, expressed as a %
C_{maxu}	Maximum unbound plasma concentration
$AUC_{u(0-t)}$	Area under the unbound plasma concentration-time curve from time 0 to time t
$AUC_{u(0-\infty)}$	Area under the unbound plasma concentration-time curve from time 0 to infinity
Cl_u/F	Apparent clearance relative to the unbound drug concentration

C_{max} and T_{max} will be obtained directly from experimental observations. If multiple maxima occur at equal concentrations, the first temporal value will be taken as the C_{max} and T_{max} .

The apparent terminal elimination half-life, $T_{1/2}$, where determinable, will be calculated as the natural log of 2 divided by the terminal phase rate constant, λ_z . The number of data points included in the regression will be determined by visual inspection, but a minimum of three data points in the terminal phase, excluding C_{max} , is required to estimate λ_z . In order for the selection to take place the adjusted r^2 value reported in Phoenix® WinNonlin® must be ≥ 0.7 .

AUC_{0-24} , AUC_{0-t} , and $AUC_{0-\infty}$ will be calculated using the linear trapezoidal linear interpolation method, using actual elapsed time values. If the actual collection time is unknown the nominal collection time may be used for the purposes of PK parameter estimation. For the purpose of calculating AUC, all missing values will be treated as missing in the PK analysis and excluded from analysis except when they occur at pre-dose where they will be set to zero. All values that were below the limit of quantitation (BLOQ) prior to T_{max} will be set to zero. BLOQ values that occur after T_{max} will be set to missing. When ≥ 2 consecutive plasma concentrations that are BLOQ are encountered after T_{max} , these and all subsequent values will be excluded from the analysis.

$AUC_{0-\infty}$ will be calculated as outlined below:

$AUC_{0-\infty} = AUC_{last} + (C_{last} / \lambda_z)$, where C_{last} is the last temporal quantifiable plasma concentration corresponding to T_{last} .

The proportion of $AUC_{0-\infty}$ due to extrapolation (AUC_{extr}) will be calculated and expressed as a percentage. $AUC_{0-\infty}$ values will be considered unreliable estimates if the AUC_{extr} is greater than 20% and will be excluded from summary tables but will be listed.

CL/F will be calculated as $Dose/AUC_{0-\infty}$.

V_z/F will be calculated as $Dose/(\lambda_z \times AUC_{0-\infty})$.

$T_{1/2}$ will be calculated as $0.693/\lambda_z$.

The fraction unbound (f_u) will be calculated as free drug concentration/total drug concentration.

The apparent clearance relative to the unbound drug concentration (Cl_u/F) will be calculated as $Cl_u/F = Dose/AUC_u$.

Listings of plasma concentrations by Subject Number, hepatic function group, and timepoint will also be provided.

To assess the effect of moderate hepatic impairment on the PK of bexagliflozin, an analyses of variance (ANOVA) with a fixed effect corresponding to the hepatic function group (normal or moderate hepatic impairment) will be fitted to the natural logarithmic transformation of PK parameters (C_{max} , AUC_{0-t} and $AUC_{0-\infty}$). The 90% confidence intervals will be constructed for the ratio of least squares (LS) geometric means of PK parameters (total and unbound C_{max} , AUC_{0-t} and $AUC_{0-\infty}$) for the moderate hepatic function group vs the normal group, with 80-125% defined as the boundaries for subjects in the PK Population.

The ratios of geometric least squares means and corresponding 90% confidence interval (CI) for the treatment comparison will be determined by exponentiating the mean differences between treatments on the logarithm scale.

The appropriateness of the mixed model will be assessed through residual analyses. Any modifications required due to poor fit will be reported and executed.

Refer to Appendix 2 for the SAS code.

Descriptive statistics of total and unbound plasma concentration time data will be summarized by hepatic function group and timepoint.

A listing of bexagliflozin concentration-time data by Subject Number, hepatic function group and timepoint will be provided.

The PK parameters C_{max} , t_{max} , λ_z , $t_{1/2}$, CL/F, V_z/F , AUC_{0-t} , AUC_{0-24} , $AUC_{0-\infty}$, AUC_{extr} , $AUC_u(0-t)$, $AUC_u(0-\infty)$, $C_{max,u}$, and Cl_u/F will be summarized by hepatic function group for bexagliflozin.

Descriptive statistics of total and unbound PK parameters will be summarized by hepatic function group for the PK Population.

Means, standard deviation (SD), medians, ranges (min, max) and geometric means and coefficients of variation will be presented for all parameters with the exception of T_{max} . Medians and ranges will be presented for T_{max} .

A listing of derived PK parameters of bexagliflozin for total and unbound bexagliflozin by Subject Number and hepatic function group will be provided.

Descriptive statistics for urinary glucose concentrations, urinary glucose excretion (UGE), urinary creatinine concentrations, and urinary glucose/creatinine by hepatic function group and collection interval will be summarized for the PD Population. Because concentration values that were below the limit of quantitation (BLOQ) prior to T_{max} will be set to zero, which cannot be included in calculation of a geometric mean, then geometric means and percent CV calculated for data including BLOQ values will be based only on the subjects with non-BLOQ data

A listing of urinary PD parameters will be provided by Subject Number, hepatic function group and collection interval.

Plasma protein bound and unbound bexagliflozin will be determined by an equilibrium dialysis method. The bexagliflozin unbound fraction will be calculated for each subject by dividing the bexagliflozin concentration in the dialysate by the bexagliflozin concentration in plasma. The unbound fraction from the plasma sample at the maximum plasma concentration will be used to calculate the unbound plasma concentration at each time point prior to 24 hrs for each individual subject. The unbound fraction from the plasma sample at 24 hrs postdose will be used to calculate the unbound plasma concentration at each time point at or after 24 hrs postdose for each subject. If the unbound fraction at 24 hrs is not available, the unbound fraction at the maximum plasma concentration will be used to calculate the unbound plasma concentration at all time points.

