3.3 Study Duration and Dates

This is a single dose study. Selection and enrollment of study subjects will begin with those designated for the hepatic impairment group. A screening visit will be completed 2 to 28 days prior to study drug administration. Subjects will be admitted to the clinic the day before administration of the investigational product and will remain in the clinic for at least 48 h following administration. Subjects will return for an end-of-study examination within 13 days of the last pharmacokinetic sample collection. Each subject from the hepatic impairment group will be matched to a healthy comparator subject. For details of the schedule and nature of the investigations, see the Schedule of Events in [Appendix 1](#).

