4 STUDY POPULATION SELECTION

4.1 Study Population

The study population comprise eight subjects with hepatic impairment conforming to the Child-Pugh class B (Child-Pugh total score 7-9) and eight control subjects (healthy subjects with normal hepatic function). Each healthy control subject will be matched with an individual subject in the hepatic impairment group by age (± 10 years), weight ($\pm 10\%$), sex, and smoking status.

Eligible subjects who consent to participate in the study will be enrolled in clinical investigational sites in the United States. Study subjects will be informed of the purpose and potential risks of participation in the study.

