5.3 Selection and Timing of Dose for Each Subject

Subjects in the hepatic impairment group will be dosed first. Control subjects will be enrolled after at least one subject in the hepatic impairment group is enrolled. Each control subject will be matched with individual subject in hepatic impairment group. Each subject will receive a single oral dose of bexagliflozin tablets, 20 mg, with 240 mL of water on Day 1 (D1) after an overnight fast of at least 10 h.

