5.4 Method of Assigning Subjects to Treatment Groups and Sequences

This is an open-label, parallel-group study. An adequate number of male or female subjects with moderate hepatic impairment [Child-Pugh total score 7-9] will be enrolled to obtain eight evaluable subjects. Another adequate number of healthy subjects with normal hepatic function will be enrolled to obtain at least 8 evaluable subjects who are matched with the subjects in the moderate hepatic impairment group individually for age (± 10 years), weight ($\pm 10\%$), sex, and smoking status.

Subjects who withdraw early for safety reasons will not be replaced.

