6.9 Removal of Subjects from the Trial

The investigator must emphasize to potential subjects the importance of continued participation for the full duration of the trial during the informed consent process. Participation in the study is voluntary. A participant has the right to withdraw from the study at any moment for any reason. The investigator will be informed immediately.

The investigator has the right to terminate participation of a subject in case it is difficult to obtain blood samples, in case of violation of the protocol or in case of severe or serious adverse events.

In case a subject withdraws from the study, the study monitor will be informed immediately. If there is a medical reason for withdrawal, the volunteer should remain under the supervision of the medical investigator until satisfactory health returns.

Subjects who withdraw from the study due to adverse event(s) or other safety concerns will not be replaced.

After a decision is made to withdraw a subject, every attempt should be made to complete all required study evaluations and procedures. Reasons for all withdrawals should be recorded on the CRF.

The investigator may withdraw a subject for any of the following reasons:

- A protocol violation occurs, or
- A serious or intolerable adverse event occurs, or
- A clinically significant change in a laboratory parameter occurs, or
- The sponsor or investigator terminates the study, or
- The subject requests to withdraw from the study.

Subjects who do not complete the study but who have received investigational product should have a follow-up examination, including a complete physical examination, vital signs, ECG and clinical laboratory tests if clinically indicated according to [Section 7](#).

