9.5.2 Statistical Analysis of Pharmacokinetic Variables

Statistical analysis will be performed using Statistical Analysis Software SAS for Windows[®] (SAS Institute Inc., USA). PK parameters for bexagliflozin will be calculated using non-compartmental analyses (NCA) of plasma concentration-time data. An analyses of variance (ANOVA) with a fixed effect corresponding to the hepatic function group will be fitted to the natural logarithmic transformation of the PK parameters (C_{max} , AUC_{0-t} and $AUC_{0-\infty}$). The 90% confidence intervals will be constructed for the ratio of geometric means of PK parameters (total and unbound C_{max} , AUC_{0-t} and $AUC_{0-\infty}$). The apparent clearance relative to the unbound drug concentration (Cl_u/F) will be calculated as $Cl_u/F = Dose/AUC_u$.

Descriptive statistics of plasma concentration-time data will be summarized by hepatic function group and timepoint.

The PK parameters C_{max} , T_{max} , λ_z , $t_{1/2}$, CL/F , V_z/F , AUC_{0-t} , $AUC_{0-\infty}$, AUC_{extr} , $AUC_{u(0-t)}$ and $AUC_{u(0-\infty)}$ will be summarized by hepatic function group. Means, standard deviations, medians, ranges (min, max) and geometric means and coefficients of variation will be presented for all parameters with the exception of T_{max} . Medians and ranges will be presented for T_{max} .

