For each enrolled subject with liver dysfunction a matched control subject (healthy subject) of similar age (± 10 years), weight ($\pm 10\%$), sex, and smoking status will be enrolled.

Blood samples to characterize the PK profile of bexagliflozin will be collected at pre-dose and at 0.5, 1, 2, 3, 4, 5, 6, 8, 10, 12, 16, 24, 36, and 48 hrs post-dose.

Urine samples for PD analysis will be collected at pre-dose (-12 to 0 hr), and in the following intervals post-dose 0–12, 12–24, 24–36, and 36–48 hrs.

Plasma concentrations of bexagliflozin will be determined by a validated liquid chromatography-mass spectrometry (LC-MS/MS) assay.

The unbound fraction of bexagliflozin will be determined at the maximal plasma concentration and at 24 h (or earlier if the 24 h post-dose sample has a concentration below the limit of quantitation) postdose for each subject by an equilibrium dialysis method.

(See Protocol Sections 3.1 to 3.3 for additional details).

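### Should the PK comparison model the one-to-one matching of controls to hepatic subjects?

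*SAP*

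**What the plan says.** The matching is individual. Protocol 3.3 states "Each subject from the hepatic impairment group will be matched to a healthy comparator subject". Section 4.1 says "Each healthy control subject will be matched with an individual subject in the hepatic impairment group by age", and goes on to weight, sex and smoking status. Section 5.3 repeats it ("Each control subject will be matched with individual subject in hepatic impairment group"), as does section 5.4 ("matched with the subjects in the moderate hepatic impairment group individually for age"). The SAP Introduction carries it forward: "For each enrolled subject with liver dysfunction a matched control subject (healthy subject) of similar age".

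The analysis is by group. Protocol 9.5.2 reads "An analyses of variance (ANOVA) with a fixed effect corresponding to the hepatic function group will be fitted" to log Cmax, AUC0-t and AUC0-inf. SAP 7.2 specifies the same model, "an analyses of variance (ANOVA) with a fixed effect corresponding to the hepatic function group (normal or moderate hepatic impairment"), and asks for 90% intervals for the total and unbound parameters, set against 80-125%.

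The code in SAP Appendix 2 has the group term alone in its MODEL statement. Its description names subject as a random effect, but the code has no RANDOM statement. A subject effect with one value per subject could not be separated from the residual, and it would not represent the pair in any case. Neither document has a pair identifier or a matching covariate in any analysis, and neither says why pairing is left out.

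**The concern.** When subjects are recruited as matched pairs, the usual expectation is that the analysis respects the pairs. If the two members of a pair tend to have similar exposure, the difference in log means varies less than the group-only model assumes. The interval is then too wide for its stated level, and precision that the matching might have provided is thrown away.

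That would matter here because the interval for the ratio is the main PK comparison under the primary objective, there are only about eight subjects per group, and the sample size has no formal basis (Protocol 9.2, SAP 3.5). The apparent remedy, a pair term in the SAP, is cheap.

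**Working it through.** **Inputs.** From the documents: 8 pairs, log scale, 90% two-sided intervals. The documents state no power, precision, standard deviation or correlation, so there is no planned figure to reproduce. The log-scale SD (σ) and the within-pair correlation (ρ) are assumptions shown over a range.

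**Formulas.**
- Group-only half-width: t(0.95, 14) × s_pooled × √(2/8), with t = 1.7613.
- Paired half-width: t(0.95, 7) × s_diff / √8, with t = 1.8946.
- With equal variances, the true variance of the difference in means is 2σ²(1 − ρ)/8. The group-only model estimates about 2σ²/8.

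**Coverage.** Treating the pooled SD as having 14 df, group-only coverage is roughly P(|T14| < 1.7613/√(1 − ρ)). At ρ = 0.3 the limit is 1.7613/0.8367 = 2.105, which gives 94.6%; simulation gives 94.5%.

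**Width.** The expected sample SD is 0.9823σ on 14 df and 0.9650σ on 7 df. The mean-width multipliers are therefore 1.7613 × 0.9823 = 1.7302 and 1.8946 × 0.9650 = 1.8283. Their ratio is 1.057, so pairing starts 5.7% behind. It breaks even where 1.0567 × √(1 − ρ) = 1, that is ρ = 1 − 1/1.0567² = 0.104. On root-mean-square width, break-even is 1 − (1.7613/1.8946)² = 0.136.

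**Simulation**, 8 complete pairs, equal variances, 400,000 trials per row:

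| ρ | Group-only coverage | Mean width, paired / group-only | Trials in which the paired interval is wider |
|---|---|---|---|
| 0 | 90.1% | 1.057 | 64% |
| 0.1 | 91.6% | 1.002 | 54% |
| 0.2 | 93.0% | 0.946 | 43% |
| 0.3 | 94.5% | 0.885 | 33% |
| 0.5 | 97.1% | 0.751 | 15% |

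The paired interval covers 90% (to within 0.1 point) throughout. At ρ = −0.2, group-only coverage is 87.0% and the width ratio 1.158, so the planned interval is conservative only when ρ is positive.

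**On the ratio scale**, as the factor by which the upper limit exceeds the point estimate:
- σ = 0.25: group-only exp(1.7302 × 0.25 × 0.5) = 1.24. Paired at ρ = 0.3 is exp(1.8283 × 0.25 × √(1.4/8)) = 1.21. Paired at ρ = 0 is exp(1.8283 × 0.25 × 0.5) = 1.26.
- σ = 0.50: 1.54 group-only, 1.47 paired at ρ = 0.3.

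**Unequal variances.** If the hepatic SD is twice the control SD, the variance of a pair difference is proportional to 1 + 4 − 4ρ = 5(1 − 0.8ρ). The simulated width ratio at ρ = 0 is 1.063, so break-even is (1 − 1/1.063²)/0.8 = 0.144. Group-only coverage at ρ = 0.3 is 93.0%.

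**Broken pairs.** Pairs can be lost: in Protocol 6.9, "Subjects who withdraw from the study due to adverse event(s) or other safety concerns will not be replaced", and SAP 5.2 removes major protocol violators. With an unbounded random pair effect, Kenward-Roger adjustment and unpartnered subjects kept, the interval at ρ = 0 is 6.1% wider than group-only with 7 pairs plus one control, and 6.8% wider with 6 pairs plus two. Break-even rises to about 0.12 and 0.15.

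**The case for a change.** The best case for a change is that individual matching has already been paid for, precision is scarce with eight per group, and a supportive pair model costs only SAP wording and one variable. SAP Appendix 2 says its code will be completed after existing data are examined, and SAP 7.2 allows modifications for poor fit. Leaving pairing open could therefore make it a data-driven choice.

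Part of this stands. The coverage figures are correct under their assumptions, the paired interval keeps its level at negative correlation too, and a sentence explaining why pairing is not modelled would have helped the reader.

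The rest does not carry a change, for these reasons:
- **The gain depends on an unknown correlation.** Neither document says that age, weight, sex or smoking affects bexagliflozin exposure. The patient characteristic that Protocol 1.2 links to AUC is renal function, which is not a matching factor and is restricted by the eGFR exclusion in 4.3. Hepatic subjects may stay on stable prescription drugs while controls may take none (Protocol 5.6), and Child-Pugh scores range from 7 to 9. Pairs do not share either source of variation, so a low correlation is quite plausible.
- **Matching has a purpose without a pair term.** In a non-randomised comparison it balances the groups on those four factors however the data are analysed.
- **A supportive model would settle nothing.** With the protocol ANOVA still primary and no formal test planned (SAP 3.3), a second interval leaves the reported comparison as it is.
- **A pair model has a pitfall of its own.** With the pair variance bounded at zero, coverage falls to 87.6-88.3% at correlations of 0 to 0.1.
- **The group-only model is already fixed.** Protocol 9.5.2 and SAP 7.2 name the same model, and the modification clause concerns residual fit, not pairing.

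**Conclusion.** The observation is accurate, but it does not show an error. Protocol and SAP agree on a group-only ANOVA, and with complete pairs the ratio is identical either way. Choosing 14 degrees of freedom over 7 with eight per group is a preference that reasonable statisticians would defend.

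At correlations of 0 to 0.1, pairing gives an interval between 5.7% wider and equal on average. At 0.3 it is about 11% narrower, which moves the factor from 1.24 to 1.21 if the log-SD is 0.25. Under positive correlation the planned interval errs on the wide side, so it does not make a claim of no effect easier. Under negative correlation it would under-cover (about 87% at −0.2), but nothing in the documents suggests a negative value.

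These sizes assume 8 complete pairs and equal group variances. A more variable hepatic group reduces the benefit of pairing and raises break-even to between 0.14 and 0.15 at twice the control SD. The correlation and SD are assumed throughout. No change to the plan is needed.
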